#### Surveys and Scales:

The Tinnitus Handicap Inventory (THI) is a 25-item validated survey that evaluates the degree of impact a patient's tinnitus has on their quality of life. It is currently the first line survey for systemic impacts of tinnitus and is attached at the end of this proposal. In addition, NIH validated patient reported outcome measurement information system (PROMIS) questionnaires on anxiety, depression, physical function, and satisfaction will be administered before and after the treatment period to evaluate the collar's broader impact on patient quality of life (see end of proposal). Additionally, a custom tinnitus intensity scale modeled after the numerical pain scale with be used to assess relief. Lastly, a single item Likert scale inquiring about use of the collar when symptoms present will be applied to evaluate adherence.

# 1.4 Compliance Statement

This study will be conducted in full accordance with all applicable University of North Carolina Research Policies and Procedures and all applicable Federal and state laws and regulations All episodes of noncompliance will be documented.

The investigators will perform the study in accordance with this protocol, will obtain consent and assent, and will report unanticipated problems involving risks to subjects or others in accordance with University of North Carolina IRB Policies and Procedures and all federal requirements. Collection, recording, and reporting of data will be accurate and will ensure the privacy, health, and welfare of research subjects during and after the study.

# 2 STUDY OBJECTIVES

The purpose of the study is to determine the preliminary efficacy of an internal jugular vein compression collar for treating pulsatile tinnitus. Pilot data, if demonstrative of efficacy, will be used to apply for a multicenter grant.

# 2.1 Primary Objective (or Aim)

The primary objective of this study is to determine if an internal jugular vein compression collar can relieve symptoms of venous pulsatile tinnitus.

# 2.2 Secondary Objectives (or Aim)

The secondary objectives are to:

- Determine if the collar effect varies with time
- Evaluate changes in quality of life as a result of collar use
- Compare home use with in clinic use

# **3 INVESTIGATIONAL PLAN**

# 3.1 General Schema of Study Design

Before contact: Screen for eligibile participants through EPIC

First Visit: Consent, collect voluntary demographic and QOL data, fit collar, educate on use, evaluate symptom relief

Home Use:

#### 3.1.1 Screening Phase

Potential subjects will be screened using the protocol inclusion and exclusion criteria through EPIC. A limited waiver has been requested for this information..

#### 3.1.2 First Visit: Consent, Fitting, Education, Evaluation, Scales

During the first visit, potential participants identified through screening will be invited by a member of the study team to participate. If they agree, they will fill out consent forms, demographics, and preliminary QOL scales through REDCAP, as well as a baseline tinnitus intensity scale. At this point, a clinicial research team member not associated with their care will supervise fitting of the collar. The patient will be monitored for 10 minutes for adverse effects, then asked to complete the scale once more. Lastly, the patient will be educated on fitting and use of the collar, specifically not to use for more than 4 hours daily nor while sleeping, given the collar with its packaging and its instructions, and sent home for home use.

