#### Introduction

Tinnitus is a medical condition with a wide variety of causes that is characterized by the perception of sound, often described as ringing or buzzing, without an external stimulus.1 It is extremely common, and has a prevalence in the United States ranging from 10% to 15% of the population.2 Persistent tinnitus can have a highly negative impact on quality of life, with individuals suffering from the condition manifesting higher rates of anxiety, depression, and lowered self esteem^3-5. Pulsatile tinnitus is a specific subtype of tinnitus with limited treatment options. It is defined as a "whooshing" sound that pulsates in rhythm with the patient's heartbeat and generally manifests unilaterally. Pulsatile tinnitus affects over 10% of the total tinnitus population, and it has a variety of both vascular, specifically venous, and nonvascular causes. Unlike traditional tinnitus, medication is ineffective for most causes of pulsatile tinnitus. The provocative physical exam test for venous pulsatile tinnitus consists of the physician lightly compressing the internal jugular vein ipsilateral to the side of symptoms. For patients with any venous cause of pulsatile tinnitus, symptoms will be relieved upon compression of the ipsilateral internal jugular vein and return when pressure is released by the examiner, a diagnostic finding with 93% sensitivity. Given that the provocative exam finding for venous pulsatile tinnitus is relief of symptoms while compressing the neck, and that in many cases effective treatment options are limited for this condition, it is the goal of this study to test a FDA approved internal jugular vein compression collar as a symptomatic treatment for patients with this condition. By applying and sustaining the compression technique used by physicians on exam, it is hypothesized that this collar will achieve significant, perhaps even complete reduction in patient symptoms.

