# 3.1.4 Second Visit: Re-evaluation and Exit Scales

The participant will undergo refitting of the collar and evaluation of symptomatic relief under medical supervision once again. The participant will then complete QOL surveys again and an exit survey. This concludes participation.

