# 4.1.1 Visit 1 (at Meadowmont ENT clinic visit)

- Explanation of Study
- Invitation to participate
- Consenting of participant
- Tinnitus intensity and quality of life scales through REDCAP
- Fitting of collar
- Evaluation of pain or discomfort
- 10 minute observation of patient with fitted collar
- Readministration of tinnitus intensity scale
- Education on collar use and misuse (emphasis on no more than 4 hours daily and only while awake
- Transfer of collar and materials to participant

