#### 4.1.3 Follow up visit

Reevaluation of tinnitus baseline without collar and with collar under medical supervision

Collection of collar and instruction materials

QOL surveys through REDCAP

Qualitative Exit Survey on collar

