# 5.2 Efficacy Evaluations

#### 5.2.1 Diagnostic Tests, Scales, Measures, etc.

- Primary endpoint: symptom relief
  - Tinnitus aural intensity scale before and after collar administration at each visit and once daily for with collar and without collar intensity
- Secondary endpoint: QOL Impact
  - Tinnitus Handicap Index (Once at beginning of study, once at end)
  - Patient Reported Outcome Measurement Information System (PROMIS) scales in depression, anxiety, physical function, and satisfaction
- Secondary endpoint: Temporality
  - Aural intensity scale submissions will be plotted and compared over time course of study
- Secondary endpoint: Homes vs. clinic use
  - Supervised tinnitus intensity scale measurements will be compared to at home measurements to evaluate if perception of symptomatic intensity varies with environment

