#### 9 STUDY ADMINISTRATION

# 9.1 Treatment Assignment Methods

There will be no randomization or blinding of participants.

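### Clinic intensity is rated collar-off then collar-on with no rating after removal, so any change over the visit that is not due to the collar counts as clinic relief

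*Combined protocol and SAP*

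**What the plan says.** **Visit 1.** Section 3.1.2 has the participant complete the quality-of-life scales "as well as a baseline tinnitus intensity scale". The collar is then fitted, and: "The patient will be monitored for 10 minutes for adverse effects, then asked to complete the scale once more". The step list in 4.1.1 has the same order. After the observation period comes "Readministration of tinnitus intensity scale", followed by education and hand-over of the collar.

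**Visit 2.** Section 3.1.4 says: "The participant will undergo refitting of the collar and evaluation of symptomatic relief under medical supervision once again". Section 4.1.3 lists "Reevaluation of tinnitus baseline without collar and with collar under medical supervision", then collection of the collar. Neither section states an interval.

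**Both visits.** Section 5.2.1 gives the order as "Tinnitus aural intensity scale before and after collar administration at each visit".

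**Control.** Section 9.1: "There will be no randomization or blinding of participants". No section describes a rating after removal, a reversed order, a sham collar, or a collar-free period of equal length.

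**Use of the ratings.** Under 6.3.2 the primary endpoint averages 16 with/without pairs per participant, one from each clinic visit and one from each of 14 home days, and is tested one-sided. The supervised-versus-unsupervised endpoint compares mean relief over the two visits with mean home relief, two-sided.

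**Rationale.** For venous causes, the Introduction says "symptoms will be relieved upon compression of the ipsilateral internal jugular vein and return when pressure is released by the examiner".

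**The concern.** The clinic pairs are the only ratings taken under supervision, and they form the whole clinic side of a named secondary objective. With a fixed off-then-on order and nothing after it, the collar effect cannot be separated from anything else that changes between the two ratings, such as rest, settling into the room, natural fluctuation or practice with the scale. All of it is recorded as relief.

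The rationale also makes a prediction in two parts: relief on compression and return on release. The clinic procedure observes only the first. Return after removal would be useful supporting evidence in a pilot meant to justify a multicentre application. It is also easy to observe: the collar is collected at Visit 2, and at Visit 1 it is handed over with its packaging, which implies removal on site although the text does not say so.

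**Working it through.** The plan gives no figure for change over a visit, so there is none to reproduce on this point. The nearest stated figure, the sample size of 15.86 in 6.4, does not enter the argument. For the record, its printed substitution gives (1.96 + 0.8416)² × (4 + 4)/4 = 15.70.

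**Inputs from the documents.** 20 participants and an SD of 2 for each condition (6.4); 16 pairs, 2 of them from the clinic (6.3.2); home ratings that are daily averages with and without the collar (3.1.3), so with no fixed off-then-on order.

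**Assumptions.** Ratings fall by d points between the clinic off and on ratings for reasons other than the collar; d is taken as 0.25, 0.5 and 1.0. Home pairs carry no drift of this kind. The SD of the participant-level quantity under test is taken as 1, 2 and 2.83, the last being √(2² + 2²), the SD of a difference between two independent ratings. The clinic-versus-home test is treated as a within-participant comparison.

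**Step 1: bias.**
- Clinic relief (off minus on): d.
- Clinic minus home: d − 0 = d.
- Primary mean: (2 × d + 14 × 0)/16 = d/8, which is 0.03, 0.06 and 0.125 points for d = 0.25, 0.5 and 1.0.

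**Step 2: false-positive rate** with no true collar effect, n = 20, from the noncentral t on 19 degrees of freedom with noncentrality bias/(SD/√20). At d = 0.5 and SD = 2 the noncentrality is 0.0625/0.447 = 0.14 for the primary test and 0.5/0.447 = 1.12 for clinic versus home. Nominal level is 5% for each.

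| d | SD | Primary, one-sided | Clinic vs home, two-sided |
|---|---|---|---|
| 0.25 | 1 | 6.6% | 18.6% |
| 0.25 | 2 | 5.7% | 8.3% |
| 0.25 | 2.83 | 5.5% | 6.6% |
| 0.5 | 1 | 8.5% | 56.5% |
| 0.5 | 2 | 6.6% | 18.6% |
| 0.5 | 2.83 | 6.1% | 11.7% |
| 1.0 | 1 | 13.4% | 98.9% |
| 1.0 | 2 | 8.5% | 56.5% |
| 1.0 | 2.83 | 7.3% | 32.3% |

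**Step 3: what a rating after removal would recover.** Define clinic relief as the mean of the two off ratings minus the on rating, with no true collar effect and equally spaced ratings.
- Linear drift: the ratings are 0, −d, −2d. The mean of the off ratings is −d, and relief is −d − (−d) = 0. The bias is removed.
- Settling that levels off: the removable part starts at A and a fraction x remains after each interval, so the ratings are A, Ax, Ax². Off-on bias is A(1 − x). Off-on-off bias is A(1 + x²)/2 − Ax = A(1 − x)²/2. The ratio is (1 − x)/2. If settling is complete before the on rating (x = 0), half remains: 0.25 points for A = 0.5.

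**The case against.** The protocol openly describes a non-blinded single-cohort pilot seeking preliminary efficacy, and drift is an assumed quantity. Nothing in the documents shows that ratings fall over a visit. That stands, and it is why this is an improvement to the design rather than an error in it.

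Several stronger readings are tempting, and the documents do not support them.

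- *That the primary result is compromised.* A reader might set a 0.5-point drift against the 1-point minimum effect in 6.4 and call it half. But that effect belongs to the 16-pair endpoint, where the drift becomes 0.06 points.
- *That both visits use a 10-minute gap.* The interval is written only for Visit 1, where the gap between ratings also includes the fitting. The wording for Visit 2 suggests the same procedure but gives no time.
- *That release is never observed at all.* At home the collar is worn as needed and a without-collar average is recorded daily, so time after removal may be included. It is not a timed rating and does not test return on release, but off-collar periods after use are not wholly unobserved.
- *That a rating after removal is the only control available without a sham.* Reversing or randomising the order at a visit, or an equal collar-free period before fitting, would also be possible.
- *That it would separate the collar effect from expectation.* A participant who expects relief on compression and return on release could report both. The extra rating does not resolve that in an open-label study.

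It is also fair to object that replacing the clinic estimator outright would conflict with the 16 paired measurements in 6.3.2 and make clinic and home relief differ in definition. The extra rating therefore belongs in a sensitivity analysis.

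**Conclusion.** The point holds in a limited form. Both clinic evaluations run off then on with no rating after removal, so any change over the visit that is not due to the collar is counted as relief. The bias is d in clinic relief and in the clinic-versus-home contrast, and d/8 in the primary mean. With an assumed d of 0.5 and SD of 2, the false-positive rate is 18.6% for clinic versus home and 6.6% for the primary test, each against a nominal 5%. Over the ranges examined it runs from 6.6% to 98.9% and from 5.5% to 13.4%. These rates illustrate exposure and do not predict what will occur, since the documents give neither d nor the SD of the differences. The main exposure is one secondary comparison, together with any reading of clinic relief on its own. Separately, return on release, the second half of the protocol's rationale, is not measured under supervision. This is a cheap improvement and does not invalidate the plan.

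**What to change.** - **3.1.2/4.1.1 and 3.1.4/4.1.3:** add one intensity rating a fixed interval after the collar is removed. State the off-to-on interval and make it the same at both visits. The on-to-second-off interval should match it, because linear drift cancels only with equal spacing.
- **6.3.2:** report return on release (second off rating minus on rating) descriptively. Add a sensitivity analysis of clinic relief, and of the clinic-versus-home contrast, using the collar-on rating against the mean of the two collar-off ratings. Leave the 16 paired differences of the primary endpoint as they are.

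**Cost.** One scale item, a few more minutes per visit, and short wording changes. The extra rating is taken with the collar off, so it need not change any wear instruction. If relief persists after removal, the sensitivity estimate understates it. Settling that levels off is only partly removed (about half if it is complete before the collar-on rating), and expectation effects remain. The report should state these limits.

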# 3.1.3 At Home Use (2 weeks)

Through a REDCAP link to their email or mobile device, the participants will daily record length of time using collar, average tinnitus intensity with and without collar, and any discomfort/adversity with collar use for 14 days consecutively.

# 3.1.4 Second Visit: Re-evaluation and Exit Scales

The participant will undergo refitting of the collar and evaluation of symptomatic relief under medical supervision once again. The participant will then complete QOL surveys again and an exit survey. This concludes participation.

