# 4.2 Subject Completion/Withdrawal

Example: Subjects may withdraw from the study at any time without prejudice to their care. They may also be discontinued from the study at the discretion of the Investigator for lack of adherence to study treatment or visit schedules, development of exclusion criteria, or adverse events The Investigator or the Faculty Advisor may also withdraw subjects who violate the study plan, or to protect the subject for reasons of safety or for administrative reasons. It will be documented whether or not each subject completes the clinical study. If the Faculty Advisor becomes aware of any serious, related adverse events after the subject completes or withdraws from the study, they will be recorded in the source documents and on the CRF.

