#### 4.2.1 Early Termination Study Visit

Subjects who withdraw from the study will have all records deleted from the REDCAP database except for adverse events, which will be reported by the Faculty Advisor to the IRB.

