# 5.3 Safety Evaluation

Example: Subject safety will be monitored by observation and intervention of adverse events during the physician-supervised fitting period at the beginning of the study and by education of the participants to discontinue use of the collar with any significant change in physical well-being or onset of new symptoms and immediate reporting of that occurrence to the PI and Faculty Advisor through the REDCAP link.

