#### 6.3.2 Efficacy Analysis

The primary analysis will be based on an intention to treat approach and will include all subjects who complete the study.

The primary efficacy endpoint will be the change in tinnitus intensity with and without the collar, averaged within and across each patient's completion of the tinnitus scales. This means that there will be 16 paired collar and no collar measurements per patient, one at each clinic visit and one each day during the 14 day intervening period. The significance of this change will be evaluated using a unidirectional t-test.

Secondary endpoints will include the following:

- Temporality of symptom relief
  - Subjects with and without collar scores will be averaged for each day of the study, ANOVA testing will evaluate for the presence of a significant time component.
- Supervised vs. unsupervised use
  - The mean relief recorded at the first and second visit will be averaged and compared avross patients with the mean relief recorded during at home use using a bidirectional t test.
- QOL impacts
  - Evaluated for each scale using bidirectional t test

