# 7.1.3 Safety

Subject safety will be monitored by observation and intervention of adverse events during the physician-supervised fitting period at the beginning of the study and by education of the participants to discontinue use of the collar with any significant change in physical wellbeing or onset of new symptoms and immediate reporting of that occurrence to the PI and Faculty Advisor through the REDCAP link.

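### The plan has no rule for a participant who stops the collar for new symptoms: Visit 2 still calls for a with-collar evaluation, and a safety withdrawal could erase their non-adverse-event data

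*Combined protocol and SAP*

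**What the plan says.** All references are to the combined protocol and SAP.

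- **Stopping rule.** Section 5.3 has participants taught to "discontinue use of the collar with any significant change in physical well-being or onset of new symptoms" and to report at once through REDCap. Section 7.1.3 repeats this. Neither says whether the stop is permanent or what happens at Visit 2.
- **Visit 2.** Section 3.1.4 states: "The participant will undergo refitting of the collar and evaluation of symptomatic relief under medical supervision once again". Section 4.1.3 does not mention a refit but lists "Reevaluation of tinnitus baseline without collar and with collar under medical supervision". Its other items (collar return, quality-of-life surveys, exit survey) need no collar. Table 1 marks collar fitting at Visit 1 only, so the refit rests on 3.1.4.
- **Removal.** Under 4.2 the Investigator may discontinue a subject for adverse events, and the Investigator or Faculty Advisor "may also withdraw subjects who violate the study plan, or to protect the subject for reasons of safety".
- **Records.** Section 4.2.1: "Subjects who withdraw from the study will have all records deleted from the REDCAP database except for adverse events".
- **Analysis sets.** Section 6.3.2: "The primary analysis will be based on an intention to treat approach and will include all subjects who complete the study". Section 6.3.3 counts everyone entered at Visit 1 in the safety analysis.

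**The concern.** A participant who stops for symptoms on, say, home day 5 arrives at Visit 2 with no instruction written for their case. A clinician who follows 3.1.4 literally puts the collar back on. A clinician who declines, and uses the safety withdrawal that 4.2 offers, may set off the deletion rule. The middle course, leaving the collar off and collecting everything else, would fit the as-needed use in 4.1.2 but is not written down.

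A safety rule matters here because section 1.1 describes the device as raising intracranial volume and pressure, and 3.3.2 excludes people with known raised intracranial pressure. The halt rule tied to fitting in the synopsis covers the initial visit only.

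The data matter because the abstract names adherence, comfort and quality of life as effects to be evaluated, and people who stop for symptoms are among the most informative on these. The adverse event itself would survive, but the length-of-use entries would not. Those entries help in judging relatedness, which 6.3.3 plans to summarise. Deletion cannot be undone.

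**Working it through.** **1. Does the text lead to loss of data?** The route has four links.

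| Link | Status in the text |
|---|---|
| Participant stops for new symptoms | Instructed (5.3, 7.1.3) |
| Team declines the with-collar evaluation | Allowed by discretion (4.2, 9.4.1); no exception written in 3.1.4 or 4.1.3 |
| Team withdraws the person for safety | Allowed, not required (4.2) |
| 4.2.1 applies to withdrawal by the team | Not stated; 4.2 uses the same verb for safety removal, and 4.2.1 sits beneath it |

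If all four hold, the non-adverse-event records go. Without deletion, a withdrawn person would still be a non-completer under 6.3.2. The plan does not define whether someone who stops the collar but attends Visit 2 counts as a completer.

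**2. What one participant contributes.** Section 6.3.2 plans 16 pairs: Visit 1, 14 home days, Visit 2. For a stop on home day d, the pairs recorded so far number at most 1 + (d − 1) if no pair is recorded on the stopping day, and 1 + d if one is.

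| Home day of stopping | Pairs recorded, at most |
|---|---|
| 2 | 2–3 of 16 |
| 5 | 5–6 of 16 |
| 10 | 10–11 of 16 |
| 14 | 14–15 of 16 |

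These are upper limits, because use is as needed and some days may have no collar-on rating.

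- Withdrawn, and 4.2.1 applies: 0 pairs kept.
- Withdrawn, data to that point kept: the pairs above, plus the 5 baseline quality-of-life scores (THI and four PROMIS scales).
- Not withdrawn, followed collar-off: the pairs above, up to 1 + 14 + 1 = 16 collar-off ratings, up to 14 length-of-use entries, and (1 + 4) × 2 = 10 quality-of-life scores. The ratings and usage entries reach these totals only if daily reports continue after the stop, which the plan does not say.

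**3. How many participants?** The plan gives no stop rate. Section 3.2.2 enrols about 22 for 20 evaluable, which implies room for 2/22 = 9.1% loss, since 20/(1 − 2/22) = 22. Each participant who stops is 1/22 = 4.5%. With X ~ Binomial(22, p) and *assumed* rates:

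| Assumed stop rate p | P(X ≥ 3) |
|---|---|
| 2% | 0.009 |
| 5% | 0.095 |
| 10% | 0.380 |
| 20% | 0.846 |

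Three or more would leave fewer than 20 evaluable only if all were withdrawn and none replaced.

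**4. Price of not refitting.** One collar-on reading is lost at Visit 2: 1/16 = 6.25% of that person's pairs, but 1/2 of the supervised pairs. For the clinic-versus-home comparison 6.3.2 says "The mean relief recorded at the first and second visit will be averaged", so that person's clinic mean would rest on Visit 1 alone. A mean of 5 pairs has √(16/5) = 1.79 times the within-person standard error of a mean of 16, assuming independent days.

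**The case against.** The strongest reply is that the plan already handles the clinical side. Section 3.1.4 belongs to a general schema and describes the ordinary path. New symptoms go at once to the PI and Faculty Advisor, 9.4.1 gives the Faculty Advisor oversight of safety, 4.2 permits removal, and the Visit 2 evaluation is medically supervised. A reader might infer that the protocol requires re-exposure; read together, these sections do not support that. What stands is that supervision of a refit is not a rule about whether to refit.

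On deletion, 4.2.1 speaks of subjects who withdraw, which echoes the voluntary withdrawal in 4.2, while removal for adverse events is there called discontinuation. A reader might infer that a safety stop certainly erases a person's data. It does not: the team may simply leave the collar off, and 4.2.1 may cover voluntary withdrawal only. But 4.2 also uses withdrawal for safety removal, so the ambiguity is real.

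The consent pages and the documents filed with the IRB were not available, and device instructions go home with participants. Any of these may say more about re-use or about data after withdrawal.

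It is also fair that using pairs from people who stopped changes what the primary mean describes: relief while the collar was tolerated. That needs stating alongside the result.

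**Conclusion.** The point holds as a gap in the written rules, not as a demonstrated loss. The refit part alone is mostly clinical discretion left unwritten. The weight comes from two stated rules, deletion on withdrawal and a completers-only set labelled intention to treat. Together they can remove the participants who tolerated the collar least from the efficacy, quality-of-life and usage data.

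The size is up to all of one person's non-adverse-event records for each safety withdrawal to which 4.2.1 is applied. How often that would happen is unknown; the stop rates used above are assumptions.

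Two further inferences are tempting and unsupported. The first is that mean relief would be biased upward: people who stop for symptoms may have had full relief, so neither direction nor size can be shown. The second is that harms would be hidden: 4.2.1 keeps adverse events and 6.3.3 keeps everyone entered at Visit 1.

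The deletion and completers-only rules also reach other withdrawals; this point covers only those who stop, or are removed, for symptoms or safety.

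**What to change.** 1. **Sections 4.2 and 4.2.1.** State that stopping the collar, or investigator discontinuation or withdrawal for an adverse event or safety, does not trigger deletion, and that data collected to that point are kept.
2. **Sections 3.1.4 and 4.1.3.** State that a participant who stopped for symptoms is not refitted unless the supervising clinician documents clearance, and still completes the collar-off rating, quality-of-life scales and exit survey.
3. **Sections 3.1.3 and 4.1.2.** State that such participants continue the daily collar-off rating, with length of use recorded as 0, through day 14.
4. **Section 6.3.2.** Include them in the primary analysis using the pairs they have, note that these reflect relief during tolerated use, and report the number who stopped beside the result.

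The cost is one or two sentences in each section, with no added visits or staff. The data forms were not available, so a code for collar not applied may or may not be needed. The statistical price is the missing supervised reading and the less precise individual mean worked out above. What a participant's own decision to withdraw does to their data is left unchanged.

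### The exit quality-of-life scales follow a supervised collar session at Visit 2, whereas the baseline scales precede any collar fitting; reordering the Visit 2 forms would match the two at no cost.

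*Combined protocol and SAP*

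**What the plan says.** **Visit 1.** Section 3.1.2 has the participant complete "preliminary QOL scales through REDCAP, as well as a baseline tinnitus intensity scale", and the collar comes next: "At this point, a clinicial research team member not associated with their care will supervise fitting of the collar". The general schema in section 3.1 gives the same sequence: "Consent, collect voluntary demographic and QOL data, fit collar, educate on use, evaluate symptom relief". Section 4.1.1 lists "Tinnitus intensity and quality of life scales through REDCAP" directly ahead of the fitting. After the 10-minute observation only the intensity scale is repeated.

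**Visit 2.** Section 3.1.4 opens with the collar: "The participant will undergo refitting of the collar and evaluation of symptomatic relief under medical supervision once again". It continues: "The participant will then complete QOL surveys again and an exit survey". Section 4.1.3 lists "Reevaluation of tinnitus baseline without collar and with collar under medical supervision" first, then the return of the collar and its materials, then the quality-of-life surveys, then the qualitative exit survey.

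**Use of the scores.** Section 5.2.1 has the THI given once at the start and once at the end, and Table 1 schedules quality-of-life data only at the two visits. Section 2.2 makes the quality-of-life change resulting from collar use a secondary objective. Section 6.3.2 tests each scale with a two-sided t test; the synopsis says one-sided. Section 9.1 confirms that there is no randomization or blinding. No section gives a reason for the different order at Visit 2.

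**The concern.** A before/after change is easiest to interpret when both scores are taken under the same conditions. Here the baseline score is taken with no collar exposure at all, and the exit score is taken after a supervised collar session on the same day. The scales are self-reported by participants who know what is being tested. A participant who has just felt relief in front of staff may answer more favourably than after the home period alone; one for whom the collar has just failed or been uncomfortable may answer less favourably.

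The intended exposure is the two weeks of home use. Whatever the Visit 2 session adds or subtracts becomes part of the estimated change and would be credited to, or held against, home use. Section 2 says that the pilot data, if they show efficacy, will support a multicenter grant application, so an avoidable distortion could be carried into the next study.

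**Working it through.** **Step 1. Order of events, side by side.**

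| | Visit 1 (3.1, 3.1.2, 4.1.1) | Visit 2 (3.1.4, 4.1.3) |
|---|---|---|
| Quality-of-life scales | before the collar is fitted | after the refit and relief evaluation |
| Collar session | after the scales | before the scales |
| Collar returned | not applicable | between the evaluation and the scales (4.1.3) |
| Exit survey | none | last |

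The sections agree within each visit and differ between visits. Section 4.1.3 is a plain list, but section 3.1.4 states the sequence outright.

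**Step 2. What the design can separate.** For one scale, write

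exit − baseline = H + D + S,

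where H is the effect of home use, D is any other change over the two weeks (natural course, expectation), and S is the effect of the Visit 2 session. The plan observes one difference per participant and has no comparison group, so H, D and S cannot be told apart. A quality-of-life score taken at Visit 2 before the refit would contain H + D only. None is planned.

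**Step 3. Sensitivity of the test.** The plan gives no effect size, SD, significance level or power for quality of life, so there is no figure to reproduce.

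Inputs:
- n = 20 pairs: the evaluable number in section 3.2.2.
- Two-sided t test per scale: section 6.3.2. It is taken as paired, because each participant supplies both scores.
- α = 0.05: assumed for quality of life; section 6.4 sets it only for the principal endpoint.
- H + D = 0: assumed.
- Mean of S = d × (SD of the change score), with d = 0.1, 0.2 or 0.3: assumed, with no source in the documents.

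Under these inputs the test statistic follows a noncentral t distribution with 19 degrees of freedom and noncentrality d√20. The rejection probability is P(|T| > t₀.₉₇₅,₁₉).

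| d | d√20 | Two-sided (6.3.2) | One-sided (synopsis), favourable shift |
|---|---|---|---|
| 0 | 0 | 5.0% | 5.0% |
| 0.1 | 0.447 | 7.1% | 11.2% |
| 0.2 | 0.894 | 13.6% | 21.7% |
| 0.3 | 1.342 | 24.7% | 36.3% |

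With all 22 enrolled participants instead of 20, the two-sided figures are 7.3%, 14.6% and 26.9%.

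d is the mean shift over participants. If some shift favourably and others unfavourably, these partly cancel and the relevant d is smaller than a typical individual shift.

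**The case against.** The strongest reply is that the mechanism is weak. By Visit 2 participants have had the collar for 14 days and have been asked to rate intensity with and without it every day (3.1.3, 4.1.2). One more fitting tells them little that they do not already know, so S may be small. That stands as a limit on size; it does not remove the difference in conditions.

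Second, carry-over depends on the period that the scales ask about. The Surveys and Scales text in section 1.3 describes the THI as measuring impact on quality of life and the PROMIS scales as covering anxiety, depression, physical function and satisfaction. Neither is described as a rating of the moment. The forms were filed with the IRB and are not in the text. If they ask about a past period, a same-day event matters less. This stands too, and it is why no size can be derived.

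Third, the point concerns a secondary endpoint in a 20-person pilot. Expectation and natural change stay in the result whatever the form order, and the primary with/without-collar comparison is untouched. This is correct and sets the priority.

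Some stronger readings are tempting but unsupported:
- A reader might infer that the scales are completed minutes after relief has been demonstrated. The text speaks of evaluating relief, which may or may not occur. It gives no interval at Visit 2 (the 10 minutes belong to Visit 1), and section 4.1.3 places return of the collar in between, so the collar is probably off by then.
- A reader might infer a bias always towards benefit. An unsuccessful session would push the other way.
- A reader might take a larger shift, such as 0.5 SD (56.5% false positives, two-sided), as a forecast. Nothing in the documents supports that value or any other.
- A reader might infer that Visit 1 puts the quality-of-life scales ahead of the intensity rating. Section 3.1.2 names quality of life first and section 4.1.1 names intensity first, so that order is not settled. Only the order relative to the collar fitting is.

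**Conclusion.** The point holds as a mismatch in assessment conditions. Baseline scales precede any collar fitting, exit scales follow a supervised collar session at the same visit, and the design cannot separate that session's effect from two weeks of home use. The order of events rests on the text alone and is certain.

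The size is not known. The false-positive rates of about 7%, 14% and 25% per scale hold only for assumed mean shifts of 0.1, 0.2 and 0.3 SD, 20 pairs, a two-sided 0.05 test and no true change. They show how sensitive the test is, not how large the shift will be, which may be close to zero.

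The documents do not support concluding that the quality-of-life result is invalid, or that reordering would make the change attributable to the collar. This is a low-priority improvement to a secondary endpoint, worth making because it is free.

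**What to change.** In sections 3.1.4 and 4.1.3, state that the THI and PROMIS scales are completed at Visit 2 before the collar is refitted and relief is evaluated, as at Visit 1. Keep the qualitative exit survey on the collar at the end, where it can draw on the re-evaluation. It would also help to state the recall period of each scale in the protocol, so that a reader can judge how far same-day events could matter. The one-sided test in the synopsis and the two-sided test in section 6.3.2 need reconciling separately.

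The cost of the reordering is an edit to two sections and a change in the order of REDCap forms at one visit. It needs no extra data, staff or visit time.
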